## PROTOCOL SYNOPSIS

Protocol Title:	Prolonging the Interscalene brachial plexus block by adding liposomal bupivacaine or preservative free dexamethasone to bupivacaine: a non-inferiority trial
Protocol Number:	2019_0424
Protocol Date:	5/28/2021
Sponsor:	Department of Anesthesiology
Principal Investigator:	[name]
Objective:	The intervention being studied is the usage of liposomal bupivacaine in conjunction of standard bupivacaine in an interscalene block (ISB). It is being compared to standard bupivacaine. Does the mixture of liposomal bupivacaine and bupivacaine provide extended analgesia in comparison to bupivacaine with preservative free dexamethasone?
Study Design:	Randomized Controlled Clinical Trial
Enrollment:	112
Subject Criteria:	
 
1. Patients scheduled for elective outpatient arthroscopic shoulder surgery
 
2. ASA I-III
 
3. Ages 18 years or older
 

Data Collection:	
Sources: EPIC, Medical Records, and Patient Reported.
 
Variables: Demographics, Surgery type, Incidence of adverse effects (Horner's, hoarseness, dyspnea, hiccups), sensory exam (alcohol swab), motor exam (handgrip strength: present/weak/absent), NRS Pain scores at rest and at movement, Patient satisfaction, Opioid Consumption, Neuropraxia, Nerve Block Success, Length of PACU stay, Time to meet discharge criteria, Post Anesthetic discharge scoring system (assessed every 15 min after one hour in PACU, Brief Pain Inventory short form, LAST (local anesthetic systemic toxicity), Admission for pain.

Statistical Analysis:	
 
• Alpha level: 0.05
 
• Beta or power level: 0.8
 

---

	

• Primary outcome variable estimate (mean +/- s.d. for continuous outcome, frequency/percentage for categorical variable): Mean difference of 1.3 +/- 1.0

• Interim analysis at 50% enrollment mark

• Proposed analysis: T-Test

• Effect size or change expected between groups: Noninferior margin of 1.3

• Total sample size required: 102 + 10% (for attrition/withdrawal) = 112

--	---

## 1.0 INTRODUCTION

Liposomal bupivacaine has chemical properties that indicate that it could provide longer block duration than standard bupivacaine. In this study, patients receiving a shoulder scope will be enrolled and randomized to receive either liposomal bupivacaine and standard bupivacaine or only bupivacaine. Preservative free dexamethasone is a well-studied additive that has shown prolongation of the interscalene block (up to 22 hours) and has been well adopted as a very common clinical practice. Liposomal Bupivacaine has recently been approved by the FDA for interscalene nerve blocks. The study that was used to grant its approval compared the liposomal bupivacaine to placebo. There has yet to be a study comparing the newly approved additive to a comparable additive. Unlike other studies that compared it to placebo or a plain local anesthetic, the goal of this study is to compare liposomal bupivacaine to a long acting interscalene block with preservative free dexamethasone. Liposomal bupivacaine is being advertised as a single-shot alternative to catheters. There have been comparative studies with liposomal bupivacaine infiltration with catheters but no comparison to additives such as dexamethasone.

Rebound pain is a known phenomenon that led clinicians to seek out blocks that would last longer. Williams et al demonstrated that by prolonging the block for over 48 hours for knee surgery, it mitigates the intense rebound pain we witness with shorter acting blocks. Abdullah et al demonstrated in their meta-analysis that the interscalene block provides little benefit for shoulder surgery if the duration is less than 24 hours. There are several prospective studies, and reviews supporting preservative-free dexamethasone perineural application to prolong the block

## 2.0 OBJECTIVE(S) OF CLINICAL STUDY

If liposomal bupivacaine does not provide analgesia as adequately as the alternative (preservative-free dexamethasone bupivacaine), it will discourage its costly use. Does the mixture of liposomal bupivacaine and bupivacaine provide extended analgesia in comparison to bupivacaine with preservative free dexamethasone?

The primary outcome is average NRS pain score at rest over 72 hours (average of 3 24-hour time point [24, 48, 72 hours]).

Secondary Outcomes:

1. NRS pain scores at rest on PACU, POD1, POD2, POD3, POD4, POD7
2. NRS pain scores with movement in PACU, POD 1, POD2, POD3, POD4, POD7

3. Brief Pain Inventory short-form in PACU, POD1, POD2, POD3, POD4, POD7
4. Opioid consumption in PACU, POD1, POD2, POD3, POD4, POD 7
5. Patient Satisfaction with pain treatment in PACU, POD 1, POD 2, POD 3, POD 4, POD 7
6. Duration of analgesic block via RA phone call 24, 48, 72 hours after block placement (or longer if block continues): Patient's will be asked "Since being discharged, when did you first take an analgesic medication for shoulder pain?" and "When did your pain relief from the block completely wore off?"
7. Sensory resolution in PACU, POD1, POD2, POD3, POD4, POD7 (full resolution of block will be reported by the patient via RA phone call 24, 48, 72 hours after block placement or longer if duration continues, "When did your numbness completely resolve and returned to normal?", will likely be until POD 1, but would continue until block resolution)
8. Motor block resolution in PACU, POD1, POD2, POD3, POD4, POD7 (full resolution of block will be reported by the patient via RA phone call 24, 48, 72 hours after block placement or longer if block continues, "When did your arm or hand weakness resolve and returned to normal?", will likely be until POD 1, but would continue until block resolution)
9. Success of interscalene block: C5 Dermatome distribution will be assessed in the PACU by the anesthesiologist (co-i). Alcohol swab test (2-normal cold sensation, 1-diminished/dull, 0-absence of cold sensation). Motor test: hand grip (normal-2, weak-1, absent-0)
10. Adverse effects: sensory-motor deficits: incidence of paresthesia / neuropraxia: persistent tingling, numbness on POD7, if patient reports persistent neuropraxia after POD7, will follow up on POD14. If neuropraxia persists, will notify attending anesthesiologist and continue to follow until postoperative neurological symptoms (PONS) resolve. On POD 7, patients will be asked "on the side where surgery was performed, do you have any numbness, tingling, or weakness in the hand or fingers?"
11. If the response to continued numbness/tingling in fingers on POD7 is yes, adverse effects will be asked on POD 14.
12. Incidence of ISB related side effects: Horner's syndrome, hoarseness, hiccups, dyspnea in PACU, POD1-4,7
13. Time to readiness for PACU discharge (time of PACU admission to time of readiness to discharge, measured by Post Anesthetic Discharge Scoring System) evaluated every 15 minutes
14. Length of PACU stay (time of PACU admission to PACU discharge)

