##### 4.1.2 Secondary Endpoints

- 1. NRS pain scores at rest on PACU, POD1, POD2, POD3, POD4, POD7
- 2. NRS pain scores with movement in PACU, POD 1, POD2, POD3, POD4, POD7
- 3. Brief Pain Inventory short-form in PACU, POD1, POD2, POD3, POD4, POD7
- 4. Opioid consumption in PACU, POD1, POD2, POD3, POD4, POD 7
- 5. Patient Satisfaction with pain treatment in PACU, POD 1, POD 2, POD 3, POD 4, POD 7
- 6. Duration of analgesic block via RA phone call 24, 48, 72 hours after block placement (or longer if block continues): Patient's will be asked "Since being discharged, when did you first take an analgesic medication for shoulder pain?" and "When did your pain relief from the block completely wore off?"
- 7. Sensory resolution in PACU, POD1, POD2, POD3, POD4, POD7 (full resolution of block will be reported by the patient via RA phone call 24, 48, 72 hours after block placement or longer if duration continues, "When did your numbness completely resolve and returned to normal?", will likely be until POD 1, but would continue until block resolution)
- 8. Motor block resolution in PACU, POD1, POD2, POD3, POD4, POD7 (full resolution of block will be reported by the patient via RA phone call 24, 48, 72 hours after block placement or longer if block continues, "When did your arm or hand weakness resolve and returned to normal?", will likely be until POD 1, but would continue until block resolution)
- 9. Success of interscalene block: C5 Dermatome distribution will be assessed in the PACU by the anesthesiologist (co-i). Alcohol swab test (2-normal cold sensation, 1-diminished/dull, 0-absence of cold sensation). Motor test: hand grip (normal-2, weak-1, absent-0)
- 10. Adverse effects: sensory-motor deficits: incidence of paresthesia / neuropraxia: persistent tingling, numbness on POD7, if patient reports persistent neuropraxia after POD7, will follow up on POD14. If neuropraxia persists, will notify attending anesthesiologist and continue to

follow until postoperative neurological symptoms (PONS) resolve. On POD 7, patients will be asked “on the side where surgery was performed, do you have any numbness, tingling, or weakness in the hand or fingers?”

- 11. If the response to continued numbness/tingling in fingers on POD7 is yes, adverse effects will be asked on POD 14.
- 12. Incidence of ISB related side effects: Horner’s syndrome, hoarseness, hiccups, dyspnea in PACU, POD1-4,7

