### 6.2 Postoperative Protocol

Postop medication includes IV acetaminophen (1g IV upon PACU arrival, 750mg if <50kg), ketorolac (30mg IV q hours following intraop dose if not yet discharged, 15mg for 65 years or older, <50kg). For pain control, tramadol 50mg q 6 hours PRN (mild pain [1-3]); tramadol 100mg q hours (or 75mg if <50kg) (moderate pain [4-6]); oxycodone 5mg q 3 hours (severe pain [7-10]); dilaudid IV for rescue analgesia. Patients will be discharged with Naproxen 500mg q 12 hours, Percocet 5-325mg 1-2 tabs q 4 hours PRN, and Zofran 8mg q 8 hours.

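### One of the two questions behind block duration (secondary outcome 6) can pick up the discharge prescription or miss early PACU rescue, and no rule says which answer defines duration

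*Combined protocol and SAP*

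**What the plan says.** Section 2.0, secondary outcome 6, repeated in Section 4.1.2, measures how long the analgesic block lasts through phone calls at 24, 48 and 72 hours after block placement, or later if the block persists. Two questions are asked:

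- "Since being discharged, when did you first take an analgesic medication for shoulder pain"
- "When did your pain relief from the block completely wore off"

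Neither section says which answer is the duration, how the two combine if they disagree, or from what time duration is counted. Section 7.0 names a t-test and nothing specific to this outcome.

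Section 6.2 sets the analgesics around these questions. On going home: "Patients will be discharged with Naproxen 500mg q 12 hours, Percocet 5-325mg 1-2 tabs q 4 hours PRN, and Zofran 8mg q 8 hours". Before that, in the PACU, intravenous acetaminophen is given on arrival, ketorolac may follow, and tramadol or stronger opioids are given by pain level, up to "oxycodone 5mg q 3 hours (severe pain [7-10]); dilaudid IV for rescue analgesia".

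PACU opioid use is recorded under another secondary outcome, "Opioid consumption in PACU, POD1, POD2, POD3, POD4, POD 7". Section 6.3 lists medication usage on POD 1 to 4 and POD 7. Neither is linked to block duration.

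**The concern.** The first-analgesic question is meant to mark the moment the block stopped being enough. As worded it has two weaknesses.

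1. It accepts any analgesic. A patient who takes naproxen at the prescribed interval can truthfully report a first analgesic within about 12 hours of discharge while the block is still working. The prescription is the same in both arms, so such answers pull the arms together.
2. Its window opens at discharge. A patient who needed an opioid in the PACU, went home and next took a tablet much later gives a late answer, which looks like a long block.

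The Section 3.0 hypothesis concerns prolongation of analgesia, and outcome 6 is the item that asks patients how long their pain relief lasted. With no rule for choosing between the two answers, the weaker one could be reported as the result, or the choice could be made after the data are seen.

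**Working it through.** The documents give no expected duration, effect or power for this outcome, so there is no figure of the plan to reproduce. The check is a comparison of the texts, followed by an illustration on assumed inputs.

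**Texts side by side**

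| Feature | First-analgesic question | Wear-off question |
|---|---|---|
| What ends the duration | Any analgesic taken for shoulder pain | Patient's report that relief from the block ended |
| Window | From discharge | Not limited to after discharge |
| Depends on the discharge prescription | Can do: naproxen is every 12 hours, and only Percocet is marked as needed | No |
| Sees PACU rescue | No | Not excluded by its wording |
| Named as the defining answer | No | No |

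**How much the first answer could be diluted**

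Assumed inputs, none from the documents:

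- true time from discharge to first as-needed analgesic has mean 18 h in one arm and 30 h in the other (difference D = 12 h), SD 6 h, normal;
- a share p of patients, equal in both arms, would report a routine naproxen dose, taken at a time uniform on 0 to 12 h after discharge;
- for those patients the recorded time is the earlier of naproxen time and true time; for the rest it is the true time.

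The recorded difference is

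(1 − p) × D + p × d,

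where d is the difference that remains among patients reporting the routine dose. Simulation gives d of about 0.1 h, because nearly all of them take naproxen before the block ends.

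- p = 25%: 0.75 × 12 + 0.25 × 0.1 = 9.0 h
- p = 50%: 0.50 × 12 + 0.50 × 0.1 = 6.1 h
- p = 75%: 0.25 × 12 + 0.75 × 0.1 = 3.1 h
- p = 100%: 0.1 h

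Mixing two kinds of answer also widens the spread. At p = 25% the simulated within-arm SD rises from 6.0 h to 9.9 h, so the standardised difference falls from 12/6.0 = 2.0 to 9.0/9.9 = 0.9.

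**Sensitivity to the assumptions**

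With means of 22 h and 34 h, SD 8 h and naproxen uniform on 4 to 16 h, the recorded difference is about 9.0, 6.2, 3.3 and 0.3 h at the same four values of p. With a true difference of 6 h (22 h and 28 h, same SD and naproxen times) it is about 4.6, 3.2, 1.7 and 0.3 h. The rule that the difference shrinks by about the share p is stable across these sets. The value of p itself cannot be obtained from the documents.

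**PACU rescue**

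No size can be given, because the documents state no expected rate of opioid use in the PACU. The direction is also open: leaving out early failures flatters whichever arm has more of them.

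**The case against.** The strongest reply is that the endpoint already contains a sound measure. The wear-off question asks about the block itself and depends on no prescription. That stands. It is wrong to say that duration is read from the first analgesic alone; the gap is that nothing ranks the two answers.

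Other points on that side also carry weight:

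- A missing as-needed label is weak evidence of fixed-schedule use. In Section 6.2 the 100 mg tramadol and the oxycodone lack the label although both are tied to a pain level, and Zofran lacks it too.
- The question is restricted to medication for shoulder pain, so some patients will leave out routine doses. Others will count them, since naproxen is an analgesic prescribed after shoulder surgery. The wording does not settle it.
- PACU rescue is outside this question but not outside the data. PACU opioids and pain scores are collected, and secondary outcome 9 tests the block there.
- Outcomes 7 and 8 time the return of sensation and strength, so outcome 6 is not the only evidence on how long the block lasted.

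A reader might infer that, because dilution makes the arms look alike, it tilts the trial toward a finding of non-inferiority. The documents do not support that. The only margin, 1.3, is stated with the primary outcome estimate, and the primary outcome is the average resting pain score at 24, 48 and 72 hours. No margin or non-inferiority test is given for block duration. Nor do the documents support a claim that the difference would vanish: that needs every patient to report a routine dose.

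**Conclusion.** The concern holds in a limited form. The first-analgesic question can return an answer set by the discharge prescription and can overlook early rescue in the PACU, and the plan does not say whether it or the wear-off answer defines duration. The likely effect of routine naproxen answers is to understate a difference between the arms in this one secondary outcome, by roughly the share of patients who answer that way. That share is unknown, and every hour figure above rests on assumed inputs. The primary analysis, its margin and the sample size do not depend on this question. The repair is cheap and worth making before the outcome is analysed.

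**What to change.** Change the measurement and the definition only; no treatment changes.

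1. State in Sections 2.0 and 4.1.2 that the answer to the wear-off question, timed from block placement, defines duration of analgesia.
2. Replace the first-analgesic question with two: the date and time of the first naproxen, and the date and time of the first Percocet or other opioid taken for shoulder pain.
3. Report time from block placement to first postoperative opioid as a supportive measure, taking PACU opioid times from the chart.
4. Report it with and without PACU tramadol given for mild pain (1-3). Section 6.2 allows tramadol at that level, so counting it automatically would again let the prescription end the block.
5. Treat patients with no opioid by the end of follow-up as censored, and use Kaplan-Meier curves with a log-rank test in place of the t-test for this measure.

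The cost is a slightly longer phone script, retrieval of PACU opioid times and one time-to-event analysis. The plan lists medication usage but does not say that dose times are recorded. Patients already interviewed may therefore lack them and would contribute only the wear-off answer.

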### 5.2 Inclusion Criteria

Subjects of either gender will be included if:

1. Scheduled for elective outpatient arthroscopic shoulder surgery

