#### Pre-operative/Baseline

- DOB
- Name
- Gender
- Race
- Ethnicity
- Height, weight, BMI
- ASA
- MRN

- Preop NRS
- Preop Sensory tests
- Preop Brief Pain Inventory

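### The motor-block question in secondary outcome 8 does not separate block weakness from surgical weakness, so recorded durations may run long and the between-arm difference may be diluted

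*Combined protocol and SAP*

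**What the plan says.** Outcome 8 appears in the same form in sections 2.0 and 4.1.2 under the label of motor block resolution. The method is patient report: "full resolution of block will be reported by the patient via RA phone call 24, 48, 72 hours after block placement", or later if the block lasts longer. The question put to the patient is "When did your arm or hand weakness resolve and returned to normal". On timing, the item says resolution "will likely be until POD 1, but would continue until block resolution".

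The population (section 5.2) is patients "Scheduled for elective outpatient arthroscopic shoulder surgery".

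Three other items touch the same ground with narrower wording:

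- Outcome 6, on analgesic duration, names the cause: "When did your pain relief from the block completely wore off".
- The POD 7 deficit question in outcome 10 is limited by site: "do you have any numbness, tingling, or weakness in the hand or fingers".
- The PACU assessment in outcome 9 uses grip: "Motor test: hand grip (normal-2, weak-1, absent-0".

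The baseline list in section 6.3 includes "Preop Sensory tests" but no motor or weakness item. Section 7.0 names a t-test as the proposed analysis, beside the primary-outcome sample size inputs. No analysis is specified for outcome 8.

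**The concern.** The outcome is named for the block, but the question asks about the limb. An operated shoulder can leave the arm weak through pain, repair or immobilisation after the block has gone. That is general clinical knowledge; the documents do not say it. A patient who answers the question as worded may then report recovery from surgery instead of recovery from the block.

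Nothing else in the plan separates the two causes. After discharge the information comes by telephone, no later examination is described, and no preoperative motor baseline is listed.

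The trial is about prolonging an interscalene block, so readers will take a published motor-block duration at face value. At stake are the absolute duration in each arm and the ability to see a real difference between the arms.

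**Working it through.** **Step 1: direction.** The plan states no figure that could be reproduced here. Read literally, for each patient,

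recorded time = max(block recovery time, surgical recovery time).

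This can equal or exceed the true block time but never fall below it. A patient whose weakness has not resolved cannot say when it did, so that value is open-ended. The plan does not say how to handle it.

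**Step 2: effect on the difference.** All inputs in this step are assumed. True block times are normal with means 24 h and 36 h and SD 8 h. A share p of patients in each arm has surgical weakness lasting uniformly 24 to 168 h. Simulation gives:

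| p | Mean, 24 h arm | Mean, 36 h arm | Difference in means | Difference in medians |
|---|---|---|---|---|
| 0 | 24.0 | 36.0 | 12.0 | 12.0 |
| 10% | 31.2 | 42.1 | 10.9 | 11.9 |
| 25% | 42.0 | 51.1 | 9.2 | 11.6 |
| 50% | 60.0 | 66.5 | 6.5 | 9.7 |

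Both means rise and the difference shrinks. It does not grow. Medians hold up much better.

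**Step 3: effect on power.** The group size of 51 is from section 7.0. A mean of 22 h borrows the figure in section 1.0 for the dexamethasone block, which is stated there as an upper value, so its use as a mean is an assumption. The 28 h mean, the SD of 8 h, p and the recorded values of 168 h (7 × 24, POD 7) and 96 h (4 × 24, POD 4) are also assumed.

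For p = 10% recorded at 168 h:

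- Means: 0.9 × 22 + 0.1 × 168 = 36.6 h and 0.9 × 28 + 0.1 × 168 = 42.0 h. The difference is 5.4 h instead of 6 h.
- Variances: 0.9 × 64 + 0.09 × 146² = 1,976 and 0.9 × 64 + 0.09 × 140² = 1,822.
- SE = √((1,976 + 1,822)/51) = 8.63 h, so difference/SE = 0.63 and two-sided power at 0.05 is about 10%.
- Without contamination: SE = √(128/51) = 1.58 h, 6/1.58 = 3.79, power about 96%.

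For p = 10% recorded at 96 h, the variances are 57.6 + 0.09 × 74² = 550 and 57.6 + 0.09 × 68² = 474. SE = √(1,024/51) = 4.48 h, the ratio is 1.21, and power is about 23% (23–24% by simulation).

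The median of the contaminated 22 h arm is the 0.5/(1 − p) quantile of the true distribution. At p = 10% that is the 0.556 quantile, 22 + 8 × 0.14 = 23.1 h.

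Results with affected patients recorded at 168 h (means and medians by these formulas, powers by simulation):

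| p | Mean, 22 h arm | Median, 22 h arm | t-test power | Rank-test power |
|---|---|---|---|---|
| 0 | 22.0 h | 22.0 h | 96% | about 95% |
| 5% | 29.3 h | 22.5 h | 17% | about 91% |
| 10% | 36.6 h | 23.1 h | 10% | about 83% |
| 20% | 51.2 h | 24.5 h | 7% | about 62% |

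The mean and the t-test are very sensitive to a few long values. The median and the rank test are much less so.

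**The case against.** A reader might infer that surgical weakness will be counted as block, that duration is overstated as a matter of fact, and that a real difference between the arms will be hidden. The documents do not support going that far, for five reasons.

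- **Frequency is unknown.** The documents give neither the frequency nor the duration of surgical weakness. The item is labelled as block resolution, its calls continue only while the block does, and section 6.3 uses a block-resolution label for POD 1 to 4. The full call script is not in the documents, so some patients and callers may answer for the block alone. This stands: the claim is that duration may be overstated.
- **168 h is not a value the plan would record.** A patient still weak on POD 7 has no resolution time. Section 6.3 also lists block resolution for POD 1 to 4 but not for POD 7, whereas outcome 8 names POD 7. This stands: 168 h is only a device for sizing the effect, and the plan leaves unresolved cases undefined.
- **The loss of power depends largely on the test.** No test is specified for outcome 8, and a rank test keeps about 83% power at p = 10%. This stands, although the only test the plan names anywhere is the t-test.
- **No arm is favoured.** Patients are randomised and all have arthroscopic shoulder surgery, so the error is expected to be alike in both arms. A chance imbalance in procedure could mimic a difference, but type of shoulder surgery is recorded (section 6.3) and can be checked and adjusted for.
- **Asking about the arm is not plainly wrong.** The injection lies between the C5 and C6 roots (section 6.1). The gap is the missing attribution to the block.

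None of this removes the ambiguity. The protocol avoids it in outcome 6 by naming the block and in outcome 10 by limiting the site; outcome 8 does neither.

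**Conclusion.** The concern holds as a measurement weakness in one secondary outcome. The question in outcome 8 does not distinguish block weakness from surgical weakness. Absolute motor-block duration may therefore be overstated in both arms and the difference between them diluted, with no expected bias toward either.

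The size cannot be fixed from the documents. It rests on an assumed share of affected patients, assumed recorded times and assumed true durations. With 10% affected and recorded at 96 to 168 h, t-test power falls to about 10–24%, while a rank test and the median are only modestly affected.

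Severity is minor to moderate. The primary endpoint (rest NRS averaged over 24, 48 and 72 hours), the non-inferiority margin and the sample size do not depend on this item.

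**What to change.** In item 8 of sections 2.0 and 4.1.2, and in the call script:

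1. Tie the question to the block, as item 6 does. For example: *When did the hand or arm weakness caused by the nerve block wear off?*
2. Ask separately when hand or finger weakness ended, in line with the POD 7 question and the PACU grip test.
3. Record weakness that the patient attributes to the surgery as a separate yes/no item on the same call, not as block duration.
4. State that unresolved cases are censored at last contact, and make section 6.3 agree with outcome 8 on whether block resolution is asked on POD 7.
5. Flag any answers already collected under the present question.

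The cost is a change to one question, two short added items and matching protocol text, with no extra visits or patients. The main downside is that patients must judge the cause of their weakness, and some will judge wrongly. Outcome 6 already asks this of them for pain relief, and the hand or finger item gives a check that depends less on that judgement.

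### The POD7 question asks about weakness, but the item 10 symptom list and the item 11 POD14 trigger do not name it, so the rule for isolated hand weakness is inconsistent

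*Combined protocol and SAP*

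**What the plan says.** Section 2.0 of the combined protocol and SAP lists the secondary outcomes, and section 4.1.2 repeats them. Two items deal with neurological symptoms after the block.

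- **Item 10, heading:** "Adverse effects: sensory-motor deficits".
- **Item 10, symptom list:** "incidence of paresthesia / neuropraxia: persistent tingling, numbness on POD7".
- **Item 10, follow-up:** "if patient reports persistent neuropraxia after POD7, will follow up on POD14".
- **Item 10, escalation:** "If neuropraxia persists, will notify attending anesthesiologist and continue to follow until postoperative neurological symptoms (PONS) resolve".
- **Item 10, wording put to the patient at POD7:** "do you have any numbness, tingling, or weakness in the hand or fingers", about the operated side.
- **Item 11, POD14 rule:** "If the response to continued numbness/tingling in fingers on POD7 is yes, adverse effects will be asked on POD 14".

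Section 4.1.2 opens its item 11 with the same condition, "If the response to continued numbness/tingling in fingers on POD7 is yes", so nothing there corrects section 2.0.

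Three other places touch on the subject. Item 8 (motor block resolution) asks "When did your arm or hand weakness resolve and returned to normal". Section 6.3 lists side effects at both POD7 and POD14 without defining a case or a trigger. Section 8.0 says that every adverse event will appear in the final report.

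**The concern.** The question put to the patient is wider than the definition and the rule that use its answer. A yes that rests on weakness alone has no stated consequence under the listed symptoms or the item 11 trigger.

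Two things depend on this. The first is counting: the incidence of neuropraxia is a listed secondary outcome, and the same POD7 answer could be scored as a case or not according to which sentence staff apply. The second is follow-up: the POD14 contact, and the later notice to the attending anesthesiologist, are the plan's explicit route for a persisting deficit after an interscalene block. A motor symptom should have a clear place on that route.

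**Working it through.** No arithmetic applies, and the plan gives no figure to reproduce. The check is to compare the terms used in each place.

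| Place (sections 2.0 and 4.1.2) | Numbness | Tingling | Weakness | Site named |
|---|---|---|---|---|
| POD7 question (item 10) | yes | yes | yes | hand or fingers |
| Symptom list (item 10) | yes | yes | no | none |
| POD14 trigger (item 11) | yes | yes | no | fingers only |

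Weakness appears in one of the three, and the hand is missing from the trigger.

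Now take a patient at POD7 with hand weakness and no sensory symptom.

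1. *POD7 question.* The answer is yes, because weakness in the hand is asked about by name.
2. *Item 10 case.* The listed symptoms are both sensory. The patient has neither and, read literally, is not counted.
3. *Item 10 follow-up and escalation.* Both depend on neuropraxia persisting. The term is not defined beyond the sensory list, so on the literal reading neither step applies.
4. *Item 11.* The condition is numbness or tingling in the fingers. It is not met.

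On the broader reading, the item 10 heading brings motor deficits into neuropraxia, or item 11 is taken to mean any yes to the combined question. The patient is then counted and contacted at POD14. The text leaves both readings open.

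Next, could another section supply the missing link?

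- *Item 8* measures how long the motor block lasts and continues until it resolves. It does not feed the neuropraxia count, the POD14 contact or the notice to the attending. It names POD7 as a time point, but the POD7 list in section 6.3 omits block resolution, which is listed for POD1 to POD4.
- *Section 6.3* places side effects at POD14 but does not say which patients are asked.
- *Section 8.0* concerns reporting and starts no follow-up.

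None of them supplies the trigger or the notice.

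**The case against.** The strongest reply is that the narrow reading is strained. The POD7 question is a single combined item, and item 11 follows directly and refers to a response. The natural reading is that it means the response to that question, with the sensory terms as shorthand. To leave out a patient with isolated weakness, staff would have to split a combined answer, which the plan never tells them to do. The item 10 heading, its own follow-up sentence and the wording about postoperative neurological symptoms all point to a broad intent. If any yes is treated as the trigger, nobody is missed.

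Much of this stands. It makes the broader intent plausible and keeps the point small. It does not remove the point, because item 11 names particular symptoms and a particular site where it could have said any yes, and item 10 lists only sensory symptoms beneath its heading.

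A reader might also infer that weakness would go unrecorded. The documents do not support that. The POD7 question captures it, item 8 asks about arm or hand weakness until the block resolves, and section 8.0 commits to reporting all adverse events. What is missing is narrower: an unambiguous case definition, and the explicit link to POD14 contact and notice to the attending.

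**Conclusion.** The inconsistency is real and minor. Taken literally, items 10 and 11 leave isolated hand weakness at POD7 outside the neuropraxia count and outside the POD14 route, although the question asks about it and the heading suggests it was meant to be included.

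No size can be given. The documents state no incidence of isolated weakness and do not describe how staff would apply the rule. If they act on any yes, the effect is nil.

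It would be wrong to infer harm to the main result or a tilt between the arms. The primary outcome is the average resting pain score over 72 hours, which does not use this item, and the same wording applies to both groups. The conclusion rests only on the text of items 10 and 11 and on the absence of an overriding definition elsewhere in the document.

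**What to change.** Make the same two edits in sections 2.0 and 4.1.2.

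1. **Item 10:** define the event as persistent weakness, numbness or tingling affecting the hand or fingers, so that it matches the POD7 question.
2. **Item 11:** trigger the POD14 inquiry on any yes to that question.

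The existing sentences on follow-up and on notifying the attending anesthesiologist can then stay as they are, because the event they refer to will include weakness. The cost is a few words in each section and possibly a few more POD14 calls.
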